11.1.4 Response Criteria

11.1.4.1 Evaluation of Target Lesions

Complete Response (CR): Disappearance of all target lesions. Any pathological lymph nodes (whether target or non-target) must have reduction in short axis to <10 mm.

Partial Response (PR): At least a 30% decrease in the sum of the diameters of target lesions, taking as reference the baseline sum diameters.

Progressive Disease (PD): At least a 20% increase in the sum of the diameters of target lesions, taking as reference the smallest sum on study (this includes the baseline sum if that is the smallest on study). In addition to the relative increase of 20%, the sum must also demonstrate an absolute increase of at least 5 mm. (Note: the appearance of one or more new lesions is also considered progressions).

Stable Disease (SD): Neither sufficient shrinkage to qualify for PR nor sufficient increase to qualify for PD, taking as reference the smallest sum diameters while on study.

11.1.4.2 Evaluation of Non-Target Lesions

Complete Response (CR): Disappearance of all non-target lesions and normalization of tumor marker level. All lymph nodes must be non-pathological in size (<10 mm short axis).

Note: If tumor markers are initially above the upper normal limit, they must normalize for a patient to be considered in complete clinical response.

Non-CR/Non-PD: Persistence of one or more non-target lesion(s) and/or maintenance of tumor marker level above the normal limits.

Progressive Disease (PD): Appearance of one or more new lesions and/or *unequivocal progression* of existing non-target lesions. *Unequivocal progression* should not normally trump target lesion status. It must be representative of overall disease status change, not a single lesion increase.

Although a clear progression of "non-target" lesions only is exceptional, the opinion of the treating physician should prevail in such circumstances, and the progression status should be confirmed at a later time by the review panel (or Principal Investigator).

11.1.4.3 Evaluation of New Lesions

The finding of a new lesion should be unequivocal (i.e. not due to difference in scanning technique, imaging modality, or findings thought to represent something other than tumor (for example, some 'new' bone lesions may be simply healing or flare of pre-existing lesions). However, a lesion identified on a follow-up scan in an anatomical location that was not scanned at baseline is considered new and will indicate PD. If a new lesion is equivocal (because of small size etc.), follow-up evaluation will clarify if it truly represents new disease and if PD is confirmed, progression should be declared using the date of the initial scan on which the lesion was discovered.

11.1.4.4 Evaluation of Best Overall Response

The best overall response is the best response recorded from the start of the treatment until disease progression/recurrence (taking as reference for progressive disease the smallest measurements recorded since the treatment started). The patient's best response assignment will depend on the achievement of both measurement and confirmation criteria.

For Participants with Measurable Disease (i.e., Target Disease)

Target Lesions	Non-Target Lesions	New Lesions	Overall Response	Best Overall Response when Confirmation is Required*
CR	CR	No	CR	≥4 wks Confirmation**
CR	Non-CR/Non-	No	PR	
	PD			
CR	Not evaluated	No	PR	>4 wks Confirmation**
PR	Non-CR/Non-	No	PR	≥4 wks Committation ·
	PD/not			
	evaluated			
SD	Non-CR/Non-	No	SD	De symanted at least once >4
	PD/not			Documented at least once ≥ 4 wks from baseline**
	evaluated			wks from baseffile
PD	Any	Yes or No	PD	
Any	PD***	Yes or No	PD	no prior SD, PR or CR
Any	Any	Yes	PD	

^{*} See RECIST 1.1 manuscript for further details on what is evidence of a new lesion.

Note: Participants with a global deterioration of health status requiring discontinuation of treatment without objective evidence of disease progression at that time should be reported as "symptomatic deterioration." Every effort should be made to document the objective progression even after discontinuation of treatment.

For Participants with Non-Measurable Disease (i.e., Non-Target Disease)

Non-Target Lesions	New Lesions	Overall Response
CR	No	CR
Non-CR/non-PD	No	Non-CR/non-PD*
Not all evaluated	No	not evaluated
Unequivocal PD	Yes or No	PD
Any	Yes	PD

^{* &#}x27;Non-CR/non-PD' is preferred over 'stable disease' for non-target disease since SD is increasingly used as an endpoint for assessment of efficacy in some trials so to assign this category when no lesions can be measured is not advised

11.1.5 Duration of Response

Duration of overall response: The duration of overall response is measured from the time measurement criteria are met for CR or PR (whichever is first recorded) until the first date that recurrent or progressive disease is objectively documented (taking as reference for progressive disease the smallest measurements recorded since the treatment started, or

^{**} Only for non-randomized trials with response as primary endpoint.

^{***} In exceptional circumstances, unequivocal progression in non-target lesions may be accepted as disease progression.

death due to any cause. Participants without events reported are censored at the last disease evaluation).

Duration of overall complete response: The duration of overall CR is measured from the time measurement criteria are first met for CR until the first date that progressive disease is objectively documented, or death due to any cause. Participants without events reported are censored at the last disease evaluation.

Duration of stable disease: Stable disease is measured from the start of the treatment until the criteria for progression are met, taking as reference the smallest measurements recorded since the treatment started, including the baseline measurements.

11.1.6 Survival

Overall Survival: Overall Survival (OS) is defined as the time from randomization (or registration) to death due to any cause, or censored at date last known alive.

Progression-Free Survival: Progression-Free Survival (PFS) is defined as the time from randomization (or registration) to the earlier of progression or death due to any cause. Participants alive without disease progression are censored at date of last disease evaluation.

Time to Progression: Time to Progression (TTP) is defined as the time from randomization (or registration) to progression, or censored at date of last disease evaluation for those without progression reported.

11.1.7 Response Review

Central Review will be conducted by the DF/HCC Tumor Imaging Metric Core for DF/HCC Institutions.

12. DATA REPORTING / REGULATORY REQUIREMENTS

Adverse event lists, guidelines, and instructions for AE reporting can be found in Section 7.0 (Adverse Events: List and Reporting Requirements).

12.1 Data Reporting

12.1.1 Responsibility for Data Submission

Investigative sites within DF/HCC or DF/PCC are responsible for submitting data and/or data forms to the ODQ according to the schedule set by the ODQ.

12.2 Data Safety Monitoring

The DF/HCC Data and Safety Monitoring Committee (DSMC) will review and monitor toxicity and accrual data from this study. The committee is composed of clinical specialists with experience in oncology and who have no direct relationship with the study. Information that raises any questions about participant safety will be addressed with the Overall PI and study team.

The DSMC will review each protocol up to four times a year or more often if required to review toxicity and accrual data. Information to be provided to the committee may include: up-to-date participant accrual; current dose level information; DLT information; all grade 2 or higher unexpected adverse events that have been reported; summary of all deaths occurring with 30 days of intervention for Phase I or II protocols; for gene therapy protocols, summary of all deaths while being treated and during active follow-up; any response information; audit results, and a summary provided by the study team. Other information (e.g. scans, laboratory values) will be provided upon request.

13. STATISTICAL CONSIDERATIONS

13.1 Study Design/Endpoints

This is a single-arm, two-stage phase 2 study to evaluate the response to AZD1775 in combination with cisplatin in patients with triple-negative breast cancer. The primary endpoint is to investigate objective response rate, and secondary endpoint will examine changes in pCDC2, as well as markers of checkpoint bypass, DNA damage and apoptosis in tumor tissue. Patients may have received 0-1 prior chemotherapeutic regimen for metastatic breast cancer. The number of patients with 0 prior chemotherapeutic regimen will be limited to a maximum of n = 20.

There is data to suggest that in patients with ≤ 1 prior chemotherapy for triple-negative disease, response to ranges from 10-37%. A recent study that looked at the activity of platinum therapy for first or second line treatment of metastatic triple-negative disease found an overall response rate of 25.6%. The response rate in the first line setting was 29% and in the second line setting was 12%. Another study, found a response rate of 10.3% to cisplatin monotherapy in patients who had received ≤ 1 prior line of chemotherapy.

Based on the maximum enrollment of patients receiving first line chemotherapy for metastatic triple-negative breast cancer, as rate response of no more than 20% to cisplatin alone would be anticipated. A response rate of 40% would be of clinical interest for the combination of cisplatin with AZD1775.

The study uses a Simon optimal two-stage design with a one-sided type I error of 0.1 and type II error of 0.1 (90% power) to detect the difference between null (20%) and alternative (40%) objective response rates. In the first stage, 17 patients will be entered. If there are at least 4

responses, the study will continue to stage 2 where another 20 patients will be enrolled. If there are 10 or fewer responses among the 37 patients, the regimen will be declared not worthy of further study. If there are 11 or more responses (>30%), the regimen will be declared worthy of further study in a randomized setting for patients with metastatic triple-negative breast cancer comparing cisplatin to cisplatin + AZD1775. If the true response rate is 20%, the chance the regimen is declared ineffective is approximately 90% (exact alpha=0.095). If the true response rate is 40%, the chance that the regimen is falsely declared ineffective is 10% (exact power=0.903).

13.2 Analysis of Primary Endpoints

For this phase II trial, the analysis population is all patients who initiate protocol regimen. All patients who receive at least one dose of protocol regimen will be evaluable for objective response every 6 weeks from the time of their first treatment. The primary analysis will evaluate the objective response rate per RECIST 1.1. We will estimate this percentage and a corresponding 95% confidence interval (CIs) will be calculated.

13.3 Analysis of Secondary Endpoints

PFS is defined as the time from enrollment until disease progression or death, whichever occurs first. Patients alive and free from disease progression will be considered censored. PFS will be estimated by the method of Kaplan and Meier.

The study requires paired biopsies from all patients with accessible tumor. With a sample size of 37 and assuming that 50% of them either without accessible lesions or assay failure, paired biopsy assessment are available for 18 patients. Assuming the percent of pCDC2 positive cells decreases 50% in the presence of AZD1775 and the standard deviation of pCDC2 equals to the difference, using t statistics with 1-sided alpha of 0.05, there will be 99% power to detect the change in pCDC2 pre- and post-treatment. The calculation was done using East v6.3 (Cytel Inc). Analysis plan for all biomarker data was written in section 9.1.

Difference of % CDC2	S.d. of paired difference	Power
positive cells in paired		
samples		
0.5	0.5	99%
0.5	0.75	86%
0.5	1	65%

Descriptive statistics will be used to characterize the tumor genomic profiles available for DFCI participants by disease response to therapy (response assessed by RECIST 1.1). PFS and ORR will be estimated using Kaplan-Meier methods among patients with and without certain gene mutations, respectively. The Benjamini-Hochberg procedure will be used to control the false discovery rate and address multiple comparisons.

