1. OBJECTIVES

1.1 Study Design

This is a single-arm, two-stage Phase 2 study assessing the efficacy of AZD1775, a Wee1 tyrosine kinase inhibitor, given in combination with cisplatin chemotherapy. The population to be studied will consist of approximately 35 patients with metastatic triple-negative breast cancer who have received 0 to 1 line of chemotherapy in the metastatic setting. All patients must have measurable disease at baseline and have archival tissue available. Treatment will consist of one cycle of cisplatin monotherapy (cisplatin 75 mg/m2 IV x1) followed by combination therapy of AZD1775 plus cisplatin starting 21 days later. AZD1775 will be administered as twice daily oral dosing (AZD1775 200 mg po bid) x 5 doses over 2.5 days, in combination with cisplatin 75 mg/m2 IV every 21 days. At least 10 patients will undergo a research biopsy within 5-48 hours after cisplatin monotherapy and then again within 5-8 hours after the last dose of AZD1775 in cycle 2 of cisplatin +AZD1775. Patients will undergo restaging scans every 6 weeks, those with complete responses, partial responses, and stable disease, will continue to receive study treatment. Patients with progressive disease will be taken off study.

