1.3 Secondary Objectives

The secondary objectives of the study are:

- 1) To evaluate Progression Free Survival (PFS).
- 2) To evaluate change in pCDC2 after therapy with AZD1775 in paired biopsies
- 3) Evaluate incidence of p53 mutations in tumor tissue and correlate mutational status with response
- 4) To evaluate change in markers for DNA damage (gamma-H2AX, phospho-Histone 3, and caspase 3) after exposure to cisplatin + AZD1775 compared to cisplatin therapy alone in paired biopsy samples
- 5) To evaluate the incidence BRCA1 and BRCA2 mutations, and correlate mutational status with response

- 6) To explore other possible gene mutations that may correlate with response.
- 7) To correlate next generation sequencing of tumors with participant outcomes (ORR and PFS) in DFCI participants only.

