We will access DNA sequencing data (where possible) on tumors from all DFCI participants who previously had tumor sequencing performed under the Dana-Farber Cancer Institute's "Profile" targeted sequencing panel. MGH participants and any 16-264 participants who did not previously participate on or have sequencing performed under "Profile" will be excluded from any analysis. We will use these data to investigate candidate genomic correlates of response, including tumor mutation burden and alterations in genes involved in homologous recombination, DNA damage response, and cell cycle G1/S checkpoint signaling. Mutations in G1/S checkpoint genes, such as *TP53*, *MYC*, and *CCNE1*, may enhance reliance on the Wee1-mediated G2/M checkpoint for accurate DNA repair and therefore make these tumors more susceptible to the combination of AZD1775 and cisplatin. Altogether, these existing DNA sequencing data may reveal preliminary response biomarkers to guide future DNA and RNA sequencing studies.

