9. BIOMARKER, CORRELATIVE, AND SPECIAL STUDIES

9.1 Biomarker Studies

All biomarker analyses completed on blood and tissue samples for correlative data will be exploratory.

Weel kinase is a regulator of the G2/M checkpoint. As Weel phosphorylates CDC2 in response to genotoxic insults, inhibition of CDC2 phosphorylation by a Weel inhibitor is considered a direct measure of target engagement. Under normal conditions, pCDC2 levels in tissue is quite low. Changes in pCDC2 is contingent upon pCDC2 induction by DNA damage. Patients will therefore undergo tumor biopsies after one dose of cisplatin, and then again after a dose of cisplatin + AZD1775.

Formalin-fixed, paraffin-embedded (FFPE) biopsy specimens will be subjected to immunohistochemical analyses using standard procedures for: (1) Total CDC2; (2) phospho-CDC2; (3) gamma-H2AX; (4) phospho-Histone 3; and (5) cleaved caspase 3.

For total CDC2, phospho-CDC2, phospho-Histone 3 and cleaved caspase 3, immunohistochemical sections will be scored manually and the % positive cells will be annotated; a minimum of 200 cells will be counted. Additionally, stained slides will be scanned using an Aperio ScanScope XT workstation (Aperio Technology, Inc., Vista, CA). Images will be visualized and digitally annotated (as regions of interest, ROIs) using ImageScope software (version 10.0.35.1800, Aperio Technology). The ROIs will then be analyzed using a standard

analysis algorithm to quantitate the proportion of area that is positive for staining (color deconvolution v9.0, Aperio Technology). The expected result after cisplatin/AZD1775 compared to cisplatin alone is preserved total CDC2 staining, reduced phospho-CDC2 staining, increased phospho-Histone 3 staining and increased cleaved caspase 3 staining. In phase 1 studies, in which skin biopsies were analyzed, a decrease of phospho-CDC2 in the presence of AZD1775 of at least 50% was considered to represent evidence of target engagement. In a study of AZD1775 monotherapy, increases in gamma-H2AX were seen in 3 of 5 paired biopsies. We will analyze changes in phospho-CDC2 (using this parameter alone); additionally, the change in ratio of phospho-CDC/total CDC2 will also be assessed when biopsies post-cisplatin/AZD1775 and post-cisplatin alone are compared.

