To evaluate the relationship between BRCA status and response, the data will be tabulated and Fisher's exact test will be applied, recognizing that only large differences are detectable if the overall response rate is 30% (78% power to detect response rate of 83% among BRCA+ and 20% among BRCA- assuming 15% of patients are deemed BRCA+ and data are available for all 35 patients).

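### Section 13.3 names Kaplan-Meier for objective response rate by gene mutation, although ORR is a binary proportion elsewhere and no time-to-response event, origin or censoring rule is given

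*Combined protocol and SAP*

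**What the plan says.** Secondary objective 7 in Section 1.3 reads: "To correlate next generation sequencing of tumors with participant outcomes (ORR and PFS) in DFCI participants only". Section 13.3 sets out the analysis for it: "PFS and ORR will be estimated using Kaplan-Meier methods among patients with and without certain gene mutations, respectively". The next sentence there promises Benjamini-Hochberg control of the false discovery rate, but the paragraph names no test for either endpoint.

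Elsewhere response is handled as a proportion. For the primary analysis, Section 13.2 says "We will estimate this percentage and a corresponding 95% confidence interval (CIs) will be calculated". For response by BRCA status, Section 9.1 says "the data will be tabulated and Fisher's exact test will be applied". Section 13.1 counts responders, with 11 or more of 37 needed for success.

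Two further statements bear on how a Kaplan-Meier analysis of response might be run. Section 1.1 says "Patients with progressive disease will be taken off study", and Section 11.1.4.4 says "The best overall response is the best response recorded from the start of the treatment until disease progression/recurrence".

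**The concern.** Kaplan-Meier estimates the distribution of a time to an event. Section 13.3 gives PFS an origin, an event and a censoring rule; Section 11.1.6 does the same for overall survival and time to progression, and Section 11.1.5 for duration of response. Nothing comparable exists for ORR or time to response. Duration of response cannot fill the gap, because its clock starts at response and it exists only in responders.

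The estimate therefore depends on a choice the plan does not make. Censoring a patient at progression treats that patient as still able to respond later at the rate seen in those who remain, although under Section 11.1.4.4 the patient is already a final non-responder. The resulting overstatement depends on how fast each group progresses and when its responses occur. If a mutation is linked to faster progression, the method can create a response difference that is not there, or hide a real one. That is the comparison objective 7 asks for, and Benjamini-Hochberg cannot repair a biased estimate.

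**Working it through.** **1. Is ORR a binomial proportion in this plan?** Inputs from Section 13.1: 17 patients in stage 1, continue with at least 4 responses; 37 in total, success with at least 11; response rates 20% and 40%. The probability of success at rate p is the sum over x = 4 to 17 of P(X1 = x) × P(X2 ≥ 11 − x), with X1 ~ Bin(17, p) and X2 ~ Bin(20, p).

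- p = 0.20: 0.0948 (stated 0.095)
- p = 0.40: 0.9033 (stated 0.903)

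The Fisher power in Section 9.1 (83% versus 20%, 15% of 35 BRCA-positive) comes out at 78.8% with 5 BRCA-positive patients and an assumed alpha of 0.05, against a stated 78%. Both calculations treat response as binary.

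**2. What does Kaplan-Meier give instead?** The documents contain no response or progression times by genotype and no size for the sequenced subset, so all counts below are assumed, at scans 1, 2 and 3. At each scan the survival factor is (at risk − responses)/(at risk). Responders and progressors then leave the risk set.

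*Same ORR, different response timing.* 37 patients, 11 responders (29.7%), progressions without response 10, 6, 4:

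| Responses at scans 1, 2, 3 | 1-KM, progressors censored | Result |
|---|---|---|
| 11, 0, 0 | 1 − (26/37)(16/16)(10/10) | 29.7% |
| 6, 3, 2 | 1 − (31/37)(18/21)(10/12) | 40.2% |
| 2, 4, 5 | 1 − (35/37)(21/25)(10/15) | 47.0% |

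If progressors stay at risk and nobody else is lost before the last response, the factors telescope. In the second row, (31/37)(28/31)(26/28) = 26/37, so 1-KM = 11/37 = 29.7%; the other rows give the same.

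*A false difference.* Two genotype groups of 12, each with 4 responders (2, 1, 1; ORR 33.3%):

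- slower progression (1, 1, 1): 1 − (10/12)(8/9)(6/7) = 36.5%
- faster progression (4, 2, 1): 1 − (10/12)(5/6)(2/3) = 53.7%

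The apparent gap is 53.7 − 36.5 = 17.2 points; the true gap is zero. If all four responses in the faster group came at scan 1, its estimate would be 1 − (8/12)(4/4)(2/2) = 33.3%, so response timing also drives the bias.

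*A hidden difference.* A group with 6/12 responders, all at scan 1, and progressions 3, 2, 1: 1 − (6/12)(3/3)(1/1) = 50.0%. This falls below the 53.7% of the 4/12 group, which reverses the ranking.

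**3. Simulation.** Assumed: 18 patients per group, responses at scans 1 to 3 with probabilities 0.50, 0.35 and 0.15, per-scan progression probability in non-responders from 0.2 to 0.5, progressors censored. A true ORR of 20% gives a mean 1-KM of 23% to 32%; a true ORR of 40% gives 45% to 60%.

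**The case against.** The strongest reply is that this is a drafting slip. The closing word of the sentence makes it ambiguous, Kaplan-Meier may have been meant for PFS only, and a statistician who follows the rest of the plan is unlikely to report 1-KM as a response rate. That is plausible. But then no estimator of ORR by mutation is named at all: Section 13.3 refers to Section 9.1 for biomarker analysis, and the Fisher test there is specified for BRCA status only. The same edit is needed on either reading.

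A second reply is that nothing in the plan says progressors would be censored. Complete and partial response are defined, and the response window opens at treatment start, so an event and an origin can be pieced together. Because that window closes at progression, a progressor's status is known, which favors the crude proportion. This stands in part: censoring is a natural way to run the analysis when progressors leave the study, but it is not stated, so the bias is conditional. The alternative makes Kaplan-Meier redundant, so neither choice supports using it.

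Third, the illustrations are small against sampling error. The exact 95% interval for 4/12 is 9.9% to 65.1%, which contains both 36.5% and 53.7%, and Fisher's test of 6/12 against 4/12 gives p = 0.68. That is correct, and it limits the practical effect. It does not justify adding a systematic error that differs between the groups being compared.

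Finally, the work is exploratory. Section 9.1 says "All biomarker analyses completed on blood and tissue samples for correlative data will be exploratory", and Section 2.5 gives its purpose: "these existing DNA sequencing data may reveal preliminary response biomarkers to guide future DNA and RNA sequencing studies". That bounds the importance of the point. Objective 7 is still a listed secondary objective, and its results are meant to guide later studies.

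**Conclusion.** The concern holds. As written, Section 13.3 names a method for ORR by gene mutation that conflicts with every other treatment of response in the plan and lacks the definitions needed to run it. Under one reading of the unstated rule it overstates ORR by amounts that differ between groups; under the other it adds nothing to the proportion.

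In the assumed examples the overstatement runs from zero to about 20 points (53.7 − 33.3 = 20.4), with a spurious between-group gap of 17 points. These sizes rest on invented counts and on censoring at progression; they show the mechanism and do not predict this trial's data.

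The missing tests are part of the same defect, because Benjamini-Hochberg has no p-values to act on. The consequence is confined to objective 7, in DFCI participants with existing sequencing. The primary ORR estimate and the two-stage decision are untouched. The point should be corrected before the genomic analysis is run.

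**What to change.** Replace the last two sentences of Section 13.3 with wording such as:

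> In the groups with and without each gene mutation, PFS will be summarized by the Kaplan-Meier method and compared by the log-rank test. ORR will be the proportion of responders among all treated patients in the group, with an exact binomial confidence interval, compared by Fisher's exact test; the Benjamini-Hochberg procedure will be applied across the mutation comparisons for both ORR and PFS.

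This follows the estimator in Section 13.2, the treated-patient denominator in Sections 13.2 and 13.4.2, and the test in Section 9.1. The exact interval and the log-rank test are additions: Section 13.2 does not name an interval method, and no PFS comparison is specified. The cost is two sentences and no extra data.
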